8.0 PRIMARY CLINICAL ENDPOINT

The primary analyses will first be completed using only blinded treatment groups. All outcome analyses will be performed using the intention to treat approach. The FAITH-2 study primary clinical endpoint is a composite of patient important outcomes that occur within the 12 months post-surgery follow-up period (**Table 9**). Specifically, these are limited to 1) re-operation, 2) femoral head osteonecrosis, 3) severe femoral neck malunion, and 4) nonunion.

The first analysis of clinical outcomes will be a Cox regression with main effects for implant type and supplementation, and the interaction between the two. If the interaction is not significant at $\alpha=0.05$ we will perform two independent comparisons between the treatment groups (SHS versus cancellous screws AND separately vitamin D₃ supplementation versus placebo) using the chi-square statistic and an alpha level of 0.05 for the composite of patient important outcomes (**Tables 10 and 11**).

If the interaction is significant we will keep this interaction term in all subsequent analyses, and present two hazard ratios (HRs) with 95% confidence intervals (CIs) for the surgical intervention and two HRs for the nutritional supplementation (i.e. We will report an HR for SHS versus cancellous screws in those who receive vitamin D, and a separate HR for SHS versus cancellous screws in those who receive placebo. We will also report an HR for vitamin D versus placebo in those who receive SHS, and a separate HR for vitamin D versus placebo in those who receive cancellous screws) The results will be summarized in **Table 12**. Kaplan-Meier curves will also be constructed.

Table 9: Primary Clinical Endpoint Components and Reasons for Secondary Procedures

Outcome	Definition
Unplanned Secondary Procedures (study event)	
Any unplanned surgery related to the treatment of the femoral neck fracture. Specific unplanned secondary procedures include:
 
 • Implant removal • Bone graft • Wound closure • Proximal femur osteotomy • Implant exchange – THA • Implant exchange – HA • Implant exchange – CS • Implant exchange – SHS • Implant exchange – Other IF • Soft tissue procedure • Dynamization • Osteochondroplasty

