9.1 SF-12 Health Survey

The SF-12 Health Survey is a standardized instrument to measure health-related quality of life. This self-administered, 12-item questionnaire covers eight main health domains that make up the Physical and Mental Health Composite Scores (PCS & MCS). Each domain consists of one or two questions and is scored separately from 0 (lowest level) to 100 (highest level).⁴ The SF-12 will be summarized using means and 95% CIs at 10-week, 3, 6, 9, and 12-month intervals (**Tables 13, 14, and 15**). Longitudinal models will be used to explore the effect of treatment group and time on the SF-12 patient-reported outcomes (**Figures 4-9**).

Table 13: HRQL (SF-12), According to Surgical Treatment (No Significant Interaction Between Implant Type and Supplementation Present)

Endpoint	Surgical Treatment X		Surgical Treatment Y		Total	
	N=	Mean (SD)	N=	Mean (SD)	N=	Adjusted Mean Difference (95% CI)
Physical Composite Scale (PCS) Scores						
Post-op						
10 weeks						
3 months						
6 months						
9 months						
12 months						
Mental Health Composite Scale (MCS) Scores						
Post-op						
10 weeks						
3 months						
6 months						
9 months						
12 months						

Table 14: HRQL (SF-12), According to Nutritional Supplementation (No Significant Interaction Between Implant Type and Supplementation Present)

Endpoint	Nutritional Supplementation Treatment X		Nutritional Supplementation Treatment Y		Total	
	N=	Mean (SD)	N=	Mean (SD)	N=	Adjusted Mean Difference (95% CI)
Physical Composite Scale (PCS) Scores						
Post-op						
10 weeks						
3 months						
6 months						
9 months						
12 months						
Mental Health Composite Scale (MCS) Scores						
Post-op						
10 weeks						
3 months						
6 months						
9 months						
12 months						

Figure 4: SF-12 PCS Scores Over Time by Surgical Treatment Group (No Significant Interaction Between Implant Type and Supplementation Present)

[figure not shown]

Figure 5: SF-12 MCS Scores Over Time by Surgical Treatment Group (No Significant Interaction Between Implant Type and Supplementation Present)

[figure not shown]

Figure 6: SF-12 PCS Scores Over Time by Nutritional Supplementation Group (No Significant Interaction Between Implant Type and Supplementation Present)

[figure not shown]

Figure 7: SF-12 MCS Scores Over Time by Nutritional Supplementation Group (No Significant Interaction Between Implant Type and Supplementation Present)

[figure not shown]

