Table 15: HRQL (SF-12) (Significant Interaction Between Implant Type and Supplementation Present)

Endpoint	Surgical Treatment X		Surgical Treatment Y		Nutritional Supplementation Treatment X		Nutritional Supplementation Treatment Y		Total	
	N=	Mean (SD)	N=	Mean (SD)	N=	Mean (SD)	N=	Mean (SD)	N=	Adjusted Mean Difference (95% CI)
Physical Composite Scale (PCS) Scores										
Post-op										
10 weeks										
3 months										
6 months										
9 months										
12 months										
Mental Health Composite Scale (MCS) Scores										
Post-op										
10 weeks										
3 months										
6 months										
9 months										
12 months										

Figure 8: SF-12 PCS Scores Over Time by Treatment Group (Significant Interaction Between Implant Type and Supplementation Present)

[figure not shown]
[figure not shown]

Figure 9: SF-12 MCS Scores Over Time by Treatment Group (Significant Interaction Between Implant Type and Supplementation Present)

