9.2 Hip Outcome Score

The Hip Outcome Score (HOS)⁵ measures self-reported functional status through 28 items and two subscales that pertain to activities of daily living (ADLs) or higher-level activities such as those necessary to participate in sports. Patient-reported function, measured by the HOS, will be reported as mean differences with corresponding 95% CIs and p-values. (Tables 16, 17, and 18). Longitudinal models will be used to explore the effect of treatment group and time on the HOS patient-reported outcomes (Figures 10-12).

Table 16: Summary of HOS, According to Surgical Treatment (No Significant Interaction Between Implant Type and Supplementation Present)

Endpoint	Surgical Treatment X		Surgical Treatment Y		Total	
	N=	Mean (SD)	N=	Mean (SD)	N=	Adjusted Mean Difference (95% CI)
Post-op						
10 weeks						
3 months						
6 months						
9 months						
12 months						

Table 17: Summary of HOS, According to Nutritional Supplementation (No Significant Interaction Between Implant Type and Supplementation Present)

Endpoint	Nutritional Supplementation Treatment X		Nutritional Supplementation Treatment Y		Total	
	N=	Mean (SD)	N=	Mean (SD)	N=	Adjusted Mean Difference (95% CI)
Post-op						
10 weeks						
3 months						
6 months						
9 months						
12 months						

Figure 10: HOS Over Time by Surgical Treatment Group (No Significant Interaction Between Implant Type and Supplementation Present)

[figure not shown]

Figure 11: HOS Over Time by Nutritional Supplementation Group (No Significant Interaction Between Implant Type and Supplementation Present)

[figure not shown]
[figure not shown]

Table 18: Summary of HOS (Significant Interaction Between Implant Type and Supplementation Present)

Endpoint	Surgical Treatment X		Surgical Treatment Y		Nutritional Supplementation Treatment X		Nutritional Supplementation Treatment Y		Total	
	N=	Mean (SD)	N=	Mean (SD)	N=	Mean (SD)	N=	Mean (SD)	N=	Adjusted Mean Difference (95% CI)
Post-op										
10 weeks										
3 months										
6 months										
9 months										
12 months										

Figure 12: HOS Over Time by Treatment Group (Significant Interaction Between Implant Type and Supplementation Present)

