9.4 Radiographic Fracture Healing

Table 20: Radiographic Fracture Healing

Variable	Variable	Surgical Treatment X N=	Surgical Treatment Y N=	Nutritional Supplementation X N=	Nutritional Supplementation Y N=	Total N=
Time of Radiographic Fracture Healing, mean (SD) (months)	Adjudicated Data					
Time of Radiographic Healing of Ipsilateral Femoral Shaft Fracture, mean (SD) (months)	Adjudicated Data					

Figure 13: Kaplan-Meier Curves for Radiographic Fracture Healing (Significant Interaction Between Implant Type and Supplementation Present)

[figure not shown]

Figure 14: Kaplan-Meier Curves for Radiographic Fracture Healing by Surgical Treatment Group (No Significant Interaction Between Implant Type and Supplementation Present)

[figure not shown]

Figure 15: Kaplan-Meier Curves for Radiographic Fracture Healing by Nutritional Supplementation Group (No Significant Interaction Between Implant Type and Supplementation Present)

[figure not shown]

Figure 16: Kaplan-Meier Curves for Radiographic Healing of Ipsilateral Femoral Shaft Fracture (Significant Interaction Between Implant Type and Supplementation Present)

[figure not shown]

Figure 17: Kaplan-Meier Curves for Radiographic Healing of Ipsilateral Femoral Shaft Fracture by Surgical Treatment Group (No Significant Interaction Between Implant Type and Supplementation Present)

[figure not shown]
[figure not shown]

Figure 18: Kaplan-Meier Curves for Radiographic Healing of Ipsilateral Femoral Shaft Fracture by Nutritional Supplementation Group (No Significant Interaction Between Implant Type and Supplementation Present)

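### One implant-by-supplement interaction test, on the primary composite, decides how SF-12, HOS, healing and shaft outcomes are presented; those outcomes need their own interaction estimate and a fixed main contrast

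*Combined protocol and SAP*

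**What the plan says.** SAP section 8.0 opens the efficacy analysis this way: "The first analysis of clinical outcomes will be a Cox regression with main effects for implant type and supplementation", plus their interaction. Two branches follow.

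- **Not significant:** "If the interaction is not significant at $\alpha=0.05$ we will perform two independent comparisons between the treatment groups", by chi-square, for the composite.
- **Significant:** "If the interaction is significant we will keep this interaction term in all subsequent analyses". The SAP then lists four hazard ratios, each within one level of the other factor, for example "We will report an HR for SHS versus cancellous screws in those who receive vitamin D".

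The secondary sections inherit the split through their table and figure titles.

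- **SF-12 (9.1):** Tables 13 and 14 serve the no-interaction branch. Table 15 serves the other and is titled "HRQL (SF-12) (Significant Interaction Between Implant Type and Supplementation Present)". The analysis text says only "Longitudinal models will be used to explore the effect of treatment group and time on the SF-12 patient-reported outcomes".
- **HOS (9.2):** Tables 16 and 17 against Table 18, with the same kind of model sentence.
- **Radiographic healing (9.4):** Kaplan-Meier figures in both versions, such as "Figure 13: Kaplan-Meier Curves for Radiographic Fracture Healing (Significant Interaction Between Implant Type and Supplementation Present)". Table 20 has one marginal layout and no branch.
- **Shaft procedures (9.5):** Tables 22 and 23 against Table 24, which repeats the four simple-effect hazard-ratio columns.
- **Fracture healing complications (9.3):** Table 19 has a marginal layout only.

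The protocol has no implant-by-supplement interaction test. Section 5.1 assumes that the two interventions act independently and sizes the trial for two marginal comparisons.

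**The concern.** Whether two treatments interact is a property of a particular outcome on a particular scale. A departure from multiplicative hazards for re-operation or radiographic failure does not settle whether implant and supplement are additive for mean HOS, or whether they interact for time to healing. As written, the plan lets the first question decide the second.

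This can go wrong in two ways. A significant composite result, chance included, moves other outcomes away from the marginal comparisons for which the factorial design was chosen. A non-significant result leaves an interaction on HOS, SF-12 or healing with no planned estimate, and the marginal difference is reported without any check on whether it is uniform. In both cases the estimand of a secondary outcome is selected by data from a different outcome.

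**Working it through.** **1. The plan's own sample size.** Inputs from protocol section 5.1: control rate 25%, RRR 33% (so 16.75%), two-sided alpha 0.05, and 80% power (Table 2).

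- Uncorrected n per group = [1.96·√(2·0.20875·0.79125) + 0.8416·√(0.25·0.75 + 0.1675·0.8325)]² / 0.0825² = 379.8, so 760 in total.
- With continuity correction: (379.8/4)·[1 + √(1 + 4/(379.8·0.0825))]² = 403.7, so 404 per group and **808 in total**.
- 808/0.90 = 897.8, so **898**.

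Both printed figures are reproduced. They refer to marginal comparisons of 404 against 404. With equal allocation to four groups, each cell holds 202.

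**2. How often the branch is entered by chance.** The interaction test is at alpha 0.05, so with no true interaction about 5% of trials enter the interaction branch.

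**3. What a simple effect costs in that branch.** It compares 202 with 202. The documents give no SD for SF-12 or HOS, so continuous results are in SD units.

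| | Marginal | Simple effect |
|---|---|---|
| SE = √(2/n) | √(2/404) = 0.070 SD | √(2/202) = 0.099 SD |
| Detectable at 80% power, 2.8016 × SE | 0.197 SD | 0.279 SD |

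The SE ratio is √2 = 1.41. A contrast with 80% marginal power would have Φ(2.8016/1.4142 − 1.96) = Φ(0.02) = 51% as a simple effect. Averaged over trials with no interaction, the loss is 0.05 × (80 − 51) ≈ 1.5 percentage points.

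**4. What the composite test can detect.** The protocol gives cell rates of 30%, 20% and 20%. The double-active rate is not given. I assume multiplicative effects with RRR 33%: 30%, 20.1%, 20.1% and 13.5%. Expected events at 202 per cell are 60.6, 40.6, 40.6 and 27.2, or 169 in total.

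- SE(log ratio of HRs) ≈ √(1/60.6 + 1/40.6 + 1/40.6 + 1/27.2) = 0.32.
- Ratio detectable with 80% power: exp(2.8016 × 0.32) ≈ 2.45.
- Power for a ratio of 1.5: about 24%.

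**5. What goes unestimated when the composite test is not significant.** Take an illustrative 0.5 SD interaction on a continuous secondary outcome and none on the composite. The interaction SE is √(4/202) = 0.141 SD, so that outcome's own test has power Φ(0.5/0.141 − 1.96) ≈ 94%. The chance that it would be significant while the composite test is not is about 0.94 × 0.95 ≈ 0.90. A simulation with latent correlation of 0 to 0.5 between the two outcomes also gave about 0.90.

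**6. At the size printed in the SAP.** The Table 2 shell shows 43 per surgical arm and 86 in total. At that size the detectable marginal difference is 0.60 SD and the simple effect 0.85 SD. An interaction on a continuous outcome would need about 1.2 SD (2.8016 × √(16/86)). On the composite, about 18 events would require a ratio of hazard ratios near 16.

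**7. Tables 15 and 18.** Both are labelled for the significant-interaction branch. Their columns are the two surgical and the two supplement margins, followed by one adjusted mean difference. They have no within-stratum columns, although two margins or four strata would need more than one difference. The table does not say which contrast it holds.

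**The case against.** A reader might infer that every secondary outcome loses half its information and falls from 80% to 51% power. The documents do not support that. Simple effects are written out only for hazard ratios (section 8.0 and Table 24). Tables 15 and 18 keep marginal columns, and Tables 19 and 20 have no branch. Keeping an interaction term does not itself halve precision: with balanced coding the averaged effect is estimated almost as well as before. The 80% belongs to the composite; no secondary outcome has a power calculation, and the longitudinal models are described as exploratory.

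A reader might also infer that the plan rules out looking for interaction on HOS or healing. It does not. The shell titles do not name the outcome tested, and section 8.0 speaks of clinical outcomes in the plural, so one test per outcome may have been intended. It is not written, however, and the one carry-over rule that is written points the other way.

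Nor are the outcomes unrelated. Nonunion is defined by a radiographic union score, and protocol section 1.2 links shortening to worse function and quality of life. That gives some reason for a consistent presentation. It does not make an interaction on one scale evidence of an interaction on another.

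Finally, a single prespecified test limits the number of interaction looks. That is a fair advantage, and reporting estimates with intervals rather than further branching tests keeps most of it.

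**Conclusion.** The point holds as a modest, inexpensive correction. The written rule lets the composite's interaction result choose the presentation, and for hazard ratios the estimand, of other outcomes, against the independence assumption on which the trial was sized.

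The size is limited. By chance alone the switch occurs in about 5% of trials. The 1.41-fold SE applies only where simple effects are what is reported. For SF-12 and HOS the established defect is an undefined contrast, not a demonstrated loss of precision. In the other direction, the gap is that no interaction estimate is planned for any secondary outcome when the composite test is not significant, and that test is itself weak.

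The figures assume equal cells and 808 analysed. The composite-test figures also rest on the assumed 13.5% double-active rate, and the 0.5 SD interaction is illustrative.

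**What to change.** In SAP section 8.0, limit the carry-over sentence to further analyses of the composite. For SF-12, HOS, radiographic healing and shaft outcomes, state that:

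1. the two marginal (factorial) contrasts are always the main result;
2. each outcome's own implant-by-supplement interaction estimate is reported with a 95% CI from its own model;
3. simple effects are descriptive only.

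Revise Tables 15, 18 and 24 and the paired figures to match, and name the contrast behind each adjusted mean difference.

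This needs SAP wording and table shells, with no new data and no change in sample size. The downside is a few more exploratory interaction estimates, which will be imprecise, especially if the analysed number is near the 86 shown in the SAP shell.

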9.0 SECONDARY CLINICAL ENDPOINTS

The FAITH-2 secondary clinical endpoints include 1) health-related quality of life (HRQL), 2) patient-reported function, 3) fracture healing complications, and 4) radiographic fracture healing.

9.1 SF-12 Health Survey

The SF-12 Health Survey is a standardized instrument to measure health-related quality of life. This self-administered, 12-item questionnaire covers eight main health domains that make up the Physical and Mental Health Composite Scores (PCS & MCS). Each domain consists of one or two questions and is scored separately from 0 (lowest level) to 100 (highest level).⁴ The SF-12 will be summarized using means and 95% CIs at 10-week, 3, 6, 9, and 12-month intervals (**Tables 13, 14, and 15**). Longitudinal models will be used to explore the effect of treatment group and time on the SF-12 patient-reported outcomes (**Figures 4-9**).

Table 13: HRQL (SF-12), According to Surgical Treatment (No Significant Interaction Between Implant Type and Supplementation Present)

Endpoint	Surgical Treatment X		Surgical Treatment Y		Total	
	N=	Mean (SD)	N=	Mean (SD)	N=	Adjusted Mean Difference (95% CI)
Physical Composite Scale (PCS) Scores						
Post-op						
10 weeks						
3 months						
6 months						
9 months						
12 months						
Mental Health Composite Scale (MCS) Scores						
Post-op						
10 weeks						
3 months						
6 months						
9 months						
12 months						

Table 14: HRQL (SF-12), According to Nutritional Supplementation (No Significant Interaction Between Implant Type and Supplementation Present)

Endpoint	Nutritional Supplementation Treatment X		Nutritional Supplementation Treatment Y		Total	
	N=	Mean (SD)	N=	Mean (SD)	N=	Adjusted Mean Difference (95% CI)
Physical Composite Scale (PCS) Scores						
Post-op						
10 weeks						
3 months						
6 months						
9 months						
12 months						
Mental Health Composite Scale (MCS) Scores						
Post-op						
10 weeks						
3 months						
6 months						
9 months						
12 months						

Figure 4: SF-12 PCS Scores Over Time by Surgical Treatment Group (No Significant Interaction Between Implant Type and Supplementation Present)

[figure not shown]

Figure 5: SF-12 MCS Scores Over Time by Surgical Treatment Group (No Significant Interaction Between Implant Type and Supplementation Present)

[figure not shown]

Figure 6: SF-12 PCS Scores Over Time by Nutritional Supplementation Group (No Significant Interaction Between Implant Type and Supplementation Present)

[figure not shown]

Figure 7: SF-12 MCS Scores Over Time by Nutritional Supplementation Group (No Significant Interaction Between Implant Type and Supplementation Present)

[figure not shown]

Table 15: HRQL (SF-12) (Significant Interaction Between Implant Type and Supplementation Present)

Endpoint	Surgical Treatment X		Surgical Treatment Y		Nutritional Supplementation Treatment X		Nutritional Supplementation Treatment Y		Total	
	N=	Mean (SD)	N=	Mean (SD)	N=	Mean (SD)	N=	Mean (SD)	N=	Adjusted Mean Difference (95% CI)
Physical Composite Scale (PCS) Scores										
Post-op										
10 weeks										
3 months										
6 months										
9 months										
12 months										
Mental Health Composite Scale (MCS) Scores										
Post-op										
10 weeks										
3 months										
6 months										
9 months										
12 months										

Figure 8: SF-12 PCS Scores Over Time by Treatment Group (Significant Interaction Between Implant Type and Supplementation Present)

[figure not shown]
[figure not shown]

Figure 9: SF-12 MCS Scores Over Time by Treatment Group (Significant Interaction Between Implant Type and Supplementation Present)

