4.9 Frequency and Duration of Follow-Up

Participants will be followed for a period of 12 months post-surgery (**Figure 4**). Participant follow-up visits will occur at enrollment (baseline), post-operative (24 hours to 14 days window), 6 weeks (2 week to 8 week window), 3 months (2 to 4 month window), 6 months (5 to 7 month window), 9 months (7 to 11 month window), and 12 months (11 months or greater window) post-surgery.

The **Schedule of Assessments (Table 1)** details the requirements and procedures for each visit. All study outcomes (as defined in sections 4.8.1 and 4.8.2) will be documented on the case report forms (CRFs) at each follow-up visit.

Additionally at all follow-up visits the participant will complete the SF-12 and HOS questionnaires. At the post-surgery follow-up visit participants will answer all questionnaires based on their pre-injury status. Questionnaires for subsequent follow-up visits will be answered based on the participant's current status at the time of follow-up.

For participants who have an ipsilateral femoral shaft fracture at each follow-up visit we will document: 1) the time to radiographic fracture healing of the ipsilateral femoral shaft; 2) re-operation; and 3) fracture-related complications including compartment syndrome, wound healing problems, infection (superficial or deep), hardware failure, hardware breakage, malunion, nonunion, and prolonged pain at the fracture site.

Serious adverse events (SAEs) will also be documented at each visit. X-rays of the participant's fractured hip are required at enrollment (baseline), post-surgery, and at, 6

weeks, 3 months, 6 months, 9 months, and 12 months post-surgery. As the primary outcome includes radiographic outcomes, it is important that X-rays be obtained at all follow-up visits. MRI or other advanced imaging studies are not required and may be ordered at the discretion of the attending surgeon. Clinical notes may also be requested. If additional imaging studies are obtained, they will be sent to the Methods Centre for outcome adjudication. In addition, at the 12-month follow-up visit, any re-operations that may be planned for the participant will be documented.

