8.3 Central Adjudication Committee

The CAC will be comprised of four orthopaedic surgeons with prior adjudication experience and they will independently adjudicate the following:

- Situations where eligibility is in doubt
- Radiographic characteristics and quality of the surgery
- Patient important outcomes that define the primary outcome (re-operation, femoral head osteonecrosis, severe femoral neck malunion, or nonunion)
- Fracture healing complications
- Radiographic fracture healing

All clinical sites will submit X-Rays and any additional imaging studies (such as a hip MRI or other advanced imaging studies) to be included in the adjudication process (**Figure 7**). Clinical notes may also be requested. Any disagreements between the CAC members will be resolved during regular conference calls. If consensus cannot initially be reached, additional information will be requested from the clinical site to clarify areas of uncertainty.

Table 1: Schedule of Events

Assessment	Screening	Enrollment (Baseline)	Surgery	Post-operative	Week 6	Month 3	Month 6	Month 9	Month 12
Informed Consent	X								
Medical History	X								
AP & Lateral X-Rays of Proximal Femur	X			X	X	X	X	X	X
Physical Exam/Injury Assessment	X								
Screening Form	X								
Randomization Form		X							
Pre-Operative Form		X							
Surgery (SHS or Cancellous Screws)			X						
Surgical Forms			X						
Hospital Discharge Form				X					
Vitamin D or Placebo Supplementation**				X	X	X	X		
Follow-up Visit Forms				X	X	X	X	X	X
Assessment for Re-Operations				X	X	X	X	X	X
Assessment of Fracture Healing Complications					X	X	X	X	X
Assessment of Fracture Healing					X	X	X	X	X
Hip Outcome Score (HOS)				X*	X	X	X	X	X
Short Form-12 (SF-12)				X*	X	X	X	X	X
Assessment of Fracture Healing of the Ipsilateral Femoral Shaft Fracture***					X	X	X	X	X
Assessment for Fracture-Related Adverse Events			X	X	X	X	X	X	X
Assessment for Serious Adverse Events			X	X	X	X	X	X	X
Assessment for Planned Re-operations									X

*Asks about participant’s function prior to their hip fracture.

** Nutritional supplementation will be administered upon hospital discharge or within two weeks of the participant’s surgery, whichever comes first. Ideally, participants should be administered the nutritional supplementation as soon as possible following their surgery to repair their femoral neck fracture.

***For participant’s with an ipsilateral femoral shaft fracture.

Table 2: Sample Size Estimates

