7.0 FEASIBILITY OUTCOME MEASURES

Feasibility outcomes will be analyzed using descriptive statistics, reported as count and percentage or mean and standard deviation depending on the type of variable to summarize the FAITH-2 feasibility outcomes of 1) initiation of clinical sites (locations and timelines), 2) rate of participant enrolment, 3) rate of protocol adherence (the number of errors in randomization, 4) the number of crossovers between SHS and cancellous screw treatment groups, 5) adherence to the daily vitamin D supplementation), 6) proportion of participants with complete follow-up at 12 months post-fracture, 7) and level of data quality (**Table 8**).

Table 8: Feasibility Outcomes

Feasibility Outcomes	Variable	N=
Time to Initiation of Clinical Sites, median (IQR) (months)	Clinical site initiation tracker	
Time to Enroll 60 Participants, n (months)	2.1 Q5 of first and last enrolled participant	
Rate of Protocol Adherence: Number of Errors in Randomization, n (%)	14.1 Q2	
Rate of Protocol Adherence: Number of Crossovers between SHS and CS treatment groups, n (%)	5.1 Q1, 6.1 Q1	
Rate of Protocol Adherence: Adherence to the daily vitamin D supplementation, n (%)	8.2 Q10/Q11 (6 weeks, 3 months, 6 months)	
Proportion of Participants with Complete Follow-up at 12 Months Post-Fracture, n (%)	8.1 (12 months)	
Level of Data Quality, n (%)	Completeness of CRFs	

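### SAP 9.1 and Tables 13 to 18 name a 10-week visit that is not scheduled, and do not say that the 'Post-op' SF-12 and HOS score is recalled pre-injury status or how it is used

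*Combined protocol and SAP*

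**What the plan says.** **Time points.** SAP 9.1 states: "The SF-12 will be summarized using means and 95% CIs at 10-week, 3, 6, 9, and 12-month intervals". The shells for the SF-12 (Tables 13 to 15) and the HOS (Tables 16 to 18) all use the same rows: Post-op, 10 weeks, and 3, 6, 9 and 12 months. The text of SAP 9.2 names no time points, so for the HOS the shells alone set them. Protocol 4.9 gives the early visits as "6 weeks (2 week to 8 week window), 3 months (2 to 4 month window"), and protocol Table 1 marks the SF-12 and HOS at the post-operative visit, week 6 and months 3, 6, 9 and 12. Elsewhere the SAP keeps to that schedule: Table 8 takes supplement adherence from "8.2 Q10/Q11 (6 weeks, 3 months, 6 months"), and the physiotherapy rows in 9.6 start at 6 weeks.

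**The post-operative score.** Protocol 4.9 states: "At the post-surgery follow-up visit participants will answer all questionnaires based on their pre-injury status". The footnote to the HOS and SF-12 rows of protocol Table 1 says that the form at that visit asks about "function prior to their hip fracture". The SAP repeats neither statement.

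**Reporting and model.** Each of the six shells has one difference column, "Adjusted Mean Difference (95% CI"), which spans every row including Post-op. On modelling, SAP 9.1 says: "Longitudinal models will be used to explore the effect of treatment group and time on the SF-12 patient-reported outcomes". SAP 9.2 says the same for the HOS and adds that function, "measured by the HOS, will be reported as mean differences with corresponding 95% CIs and p-values". Protocol Table 4 likewise names only treatment and time.

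**The concern.** There are two problems in the same six tables.

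The first is a time point that the trial does not have. An analyst who follows the shells has a row with no matching visit and a scheduled visit with no row.

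The second is that the SAP does not identify the content or the role of the post-operative score. Because it refers to the time before the injury, treatment cannot have affected the status it describes. Printed without a note under an adjusted-difference heading, a chance or recall imbalance could be read as an early effect of implant or supplement. It is also the only pre-injury SF-12 and HOS that protocol Table 1 schedules, so it is the natural baseline covariate. If its role is left open, that choice could be made after results are seen. Quality of life and function are the first secondary objective listed in protocol 2.2.

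**Working it through.** **1. Can 10 weeks be any scheduled visit?** The inputs are the windows in protocol 4.9.

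- 10 weeks = 70 days; 70 / 30.44 = 2.30 months.
- 6-week visit: 2 to 8 weeks = 14 to 56 days. Seventy days lies outside.
- 3-month visit: 2 to 4 months = 60.9 to 121.8 days (8.7 to 17.4 weeks). Seventy days lies inside, but that visit already has its own row.

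The SAP's 10-week time point therefore cannot be reproduced from the schedule.

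| Source | Assessments after surgery |
|---|---|
| Protocol 4.9 and Table 1 | post-operative, 6 weeks, 3, 6, 9, 12 months |
| SAP 9.1 text | 10 weeks, 3, 6, 9, 12 months |
| SAP Tables 13 to 18 | Post-op, 10 weeks, 3, 6, 9, 12 months |
| SAP Table 8 (adherence) | 6 weeks, 3, 6 months |
| SAP 9.6 (physiotherapy) | 6 weeks, 3, 6, 9, 12 months |

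**2. How many entries are affected?** Tables 13, 14 and 15 have two scores each (physical and mental composite), so 3 × 2 = 6 rows. Tables 16, 17 and 18 have one each, so 3 rows. The total is nine rows plus the sentence in 9.1.

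**3. What is in the Post-op row?** The row name matches the protocol's visit name. Its content is recalled pre-injury status, collected 24 hours to 14 days after surgery. The 9.1 sentence leaves this time point out, while Tables 13 to 15 include it.

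**4. What would the covariate gain?** Let r be the correlation between the pre-injury score and a follow-up score. The documents give no value, so a range is assumed. At one visit, the standard error relative to follow-up alone is sqrt(1 − r²):

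| r (assumed) | sqrt(1 − r²) | Reduction in SE | Detectable difference, 404 per group |
|---|---|---|---|
| no covariate | 1 | none | 0.197 SD |
| 0.2 | 0.980 | 2% | 0.193 SD |
| 0.3 | 0.954 | 5% | 0.188 SD |
| 0.5 | 0.866 | 13% | 0.171 SD |

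The last column is 2.80 × sqrt(2/404) × the relative SE, for 80% power and two-sided 5% (2.80 = 1.96 + 0.84), with 808/2 = 404 per group. The percentage reduction does not depend on sample size. It applies only if the score is not already among the unstated adjustments.

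**5. What could it cost?** Protocol 4.11 says participants cannot be blinded to implant, and the score is recalled after surgery. If recall differs between implants by d, with no matching difference in true status, adjustment shifts the estimate by about r × d. With d = 0.1 SD (assumed):

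- r = 0.3: 0.3 × 0.1 = 0.03 SD, so a true 0.30 SD could be estimated as 0.27.
- r = 0.5: 0.5 × 0.1 = 0.05 SD, so 0.30 SD could become 0.25.
- Without the covariate: 0.30 SD, no shift.

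The supplement comparison is blinded, so the risk there is smaller.

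**The case against.** The strongest defence is that these are matters of labelling. Post-op is the protocol's own visit name, and the protocol defines what is asked there. The shells are empty, and a heading that spans all rows does not prove that every cell will be filled. No scores are lost, because they are collected at 6 weeks, and an analyst who found no 10-week visit would probably relabel the row. For the implant comparison, adjusting for a score recalled by unblinded participants is a trade-off, so leaving it out would not be an error. All of this stands. What it does not answer is that the SAP gives no note on content, no definition of the adjustment and no row for a scheduled visit.

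A reader might infer more than the documents support, in three ways.

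- *That the SAP tests pre-injury status as a follow-up outcome.* If all six Post-op differences in Tables 13, 14, 16 and 17 were filled and independent, the chance of at least one 95% interval excluding zero with no true difference would be 1 − 0.95⁶, about 26%. But nothing says those cells will be filled. The 9.1 sentence omits the time point, 9.2 ties its p-values to no row, and Tables 16 to 18 have no p-value column.
- *That the SAP fails to adjust for baseline.* The column is headed as adjusted and its covariates are not listed, so the pre-injury score may be among them.
- *That the treatment effect would be diluted by pooling the pre-injury row into one treatment coefficient.* The per-visit rows make that reading unlikely.

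**Conclusion.** The point holds as an inconsistency and an omission. The 10-week time point conflicts with the protocol and with other parts of the SAP. It is probably a slip for 6 weeks, but it appears in the 9.1 text and in nine rows. The SAP does not say that the Post-op score is recalled pre-injury status, what the differences are adjusted for, or how the score enters the longitudinal models. These findings come directly from the text and need no assumption.

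The gain from naming the score as a covariate is modest: about 2%, 5% or 13% off the single-visit standard error, conditional on the assumed correlations and on the score not already being used. The possible cost for the implant comparison is a shift of about 0.03 to 0.05 SD under an assumed 0.1 SD recall difference. Only secondary outcomes are affected. The primary analysis, alpha and sample size do not change. The correction is worth making before unblinding.

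**What to change.** 1. Replace 10 weeks with 6 weeks in the SAP 9.1 text and in all nine rows of Tables 13 to 18.
2. Relabel Post-op as 'Pre-injury (recalled at the post-operative visit)' and show it descriptively by group, with no treatment difference or p-value.
3. In 9.1 and 9.2, state the model: SF-12 and HOS scores at 6 weeks and 3, 6, 9 and 12 months as outcomes, with treatment, visit, treatment-by-visit and the pre-injury score as covariate. Keep the implant-by-supplement term where SAP 8.0 requires it. List any other covariate behind the adjusted differences, or state that there is none.
4. For the surgical comparison, add a sensitivity analysis without the pre-injury score, because recall is not blinded to implant.

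The cost is SAP wording, table shells and one extra model fit per score. The data are already scheduled and no visit is added.
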